6.2 DATA SHARING PLANS

6.2.1 Human Data Sharing Plan

What data will be shared?

I will share human data generated in this research for future research as follows:

- Coded, linked data in an NIH-funded or approved public repository.
- Coded, linked data in BTRIS (automatic for activities in the Clinical Center)
- Identified or coded, linked data with approved outside collaborators under appropriate agreements.

Data will be shared through:

- An NIH-funded or approved public repository: clinicaltrials.gov, dbGaP.
- BTRIS (automatic for activities in the Clinical Center)
- Approved outside collaborators under appropriate individual agreements.
- Publication and/or public presentations.

Data will be shared:

- Before publication.
- At the time of publication or shortly thereafter.

6.2.2 Genomic Data Sharing Plan

Unlinked genomic data will be deposited in public genomic databases such as dbGaP in compliance with the NIH Genomic Data Sharing Policy.

6.3 RESPONSE CRITERIA

For the purposes of this study, patients should be re-evaluated for response every 8 weeks. Response and progression will be evaluated in this study using the iRANO (Immunotherapy Response Assessment in Neuro-oncology) criteria that provides special consideration for the development of pseudo progression, given that the treatment is designed to evoke an immune/inflammatory response. The iRANO criteria provide special considerations for immunotherapy response assessment and represent an integration with established RANO criteria. The iRANO criteria are provided and fully explained in [Appendix D](#).

6.3.1 Methods for Evaluation of Measurable Disease

All measurements should be taken and recorded in metric notation using a ruler or calipers. All baseline evaluations should be performed as closely as possible to the beginning of treatment and never more than 4 weeks before the beginning of the treatment.

The same method of assessment and the same technique should be used to characterize each identified and reported lesion at baseline and during follow-up.

Measurable Disease: Bi-dimensionally measurable lesions with clearly defined margins by GD-DPTA enhanced MRI scan. The maximal diameter and second perpendicular measurement are at least 10 mm in size.

Non-measurable disease. All other lesions (or sites of disease), including small lesions (longest diameter <10 mm), are considered non-measurable disease.

6.3.2 Response Criteria

6.3.2.1 Response Criteria: RANO Criteria with the iRANO update ([Appendix D](#))

Complete Response (CR): All of the following criteria must be met:

- Complete disappearance of all enhancing measurable and non-measurable disease sustained for at least 4 weeks. In the absence of a confirming scan 4 weeks later, this scan will be considered only stable disease.
- No new lesions.
- All measurable and non-measurable lesions must be assessed using the same techniques as baseline.
- Patients must be on no steroids or on physiologic replacement doses only.
- Stable or improved non-enhancing (T2/FLAIR) lesions
- Stable or improved clinically, for clinical signs and symptoms present at baseline and recorded to be disease related

Patients with residual non-measurable disease cannot have a complete response. The best response possible is stable disease.

Partial Response (PR): All of the following criteria must be met:

- Greater than or equal to 50% decrease compared to baseline in the sum of products of perpendicular diameters of all measurable enhancing lesions sustained for at least 4 weeks.

In the absence of a confirming scan 4 weeks later, this scan will be considered only stable disease.

- No progression of non-measurable disease.
- No new lesions.
- All measurable and non-measurable lesions must be assessed using the same techniques as baseline.
- The steroid dose at the time of the scan evaluation should be no greater than the dose at time of baseline scan.
- Stable or improved non-enhancing (T2/FLAIR) lesions on same or lower dose of corticosteroids compared to baseline scan.
- Stable or improved, for clinical signs and symptoms present at baseline and recorded to be disease related clinically.

Progressive Disease (PD): Any of the following criterion must be met:

- > 25% increase in sum of the products of perpendicular diameters of enhancing lesions (over best response [smallest tumor size] or baseline if no decrease) on stable or increasing doses of corticosteroids
- Any new enhancing measurable lesion that when added to the change in initial tumor(s) exceeds a 25% increase in cross-sectional area.
- Clear clinical deterioration not attributable to other causes apart from the tumor (e.g. seizures, medication side effects, complications of therapy, cerebrovascular events, infection, etc.). The definition of clinical deterioration is left to the discretion of the investigator but it is recommended that a decline in the Karnofsky Performance Score (KPS) from 100 or 90 to 70 or less, a decline in KPS of at least 20 from 80 or less, or a decline in KPS from any baseline to 50 or less, for at least 7 days, be considered neurologic deterioration, unless attributable to co-morbid events or changes in corticosteroid dose.
- Failure to return for evaluation due to death or deteriorating condition

Classification of progressive disease may be deferred for up to three months for patients with initial radiographic findings consistent with progressive disease (criteria a and b above) as detailed below. However, if follow-up imaging after three months confirms progression or if the patient experiences significant clinical decline at any time, the date of actual progression will be back-dated to the first date that the patient met criteria for progression and such patients should discontinue further immunotherapy.

Stable Disease (SD): All of the following criteria must be met:

- Does not qualify for CR, PR, or progression.
- All measurable and non-measurable sites must be assessed using the same techniques as baseline.
- Stable clinically.

Unknown Response Status: Progressive disease has not been documented and one or more measurable or non-measurable lesions have not been assessed.

Patients who require increased corticosteroids within two weeks of MRI assessment (relative to the dose taken at the time of the prior assessment) cannot be classified as CR, PR or SD and should be classified as non-evaluable at that time point. Conversely, patients who decrease corticosteroids within two weeks of MRI assessment (relative to the dose taken at the time of the prior assessment) cannot be classified as PD and should be classified as non-evaluable.

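### The stable-disease cap for residual non-measurable disease in 6.3.2.1 conflicts with the PR criteria in the same section, so a patient who meets every PR criterion can be scored SD

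*Combined protocol and SAP*

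**What the plan says.** Four parts of the combined protocol and SAP bear on this.

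- **The cap.** At the end of the CR criteria, 6.3.2.1 says: "Patients with residual non-measurable disease cannot have a complete response. The best response possible is stable disease".
- **The PR list.** Directly below, PR requires "Greater than or equal to 50% decrease compared to baseline in the sum of products of perpendicular diameters of all measurable enhancing lesions sustained for" a minimum of four weeks. On non-measurable disease it requires only "No progression of non-measurable disease".
- **The size definition.** Section 6.3.1 says: "All other lesions (or sites of disease), including small lesions (longest diameter <10 mm), are considered non-measurable disease".
- **Appendix D.** In the modified RANO table, the PR column asks for a decrease of 50% or more in enhancing disease. It has no entry that limits PR when non-measurable disease remains.

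On confirmation, 6.3.2.1 says of both CR and PR: "In the absence of a confirming scan 4 weeks later, this scan will be considered only stable disease". Section 6.3 says "patients should be re-evaluated for response every 8 weeks", and the Study Calendar (3.5, footnote 7) allows 7 days either side.

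Section 10.2.2 restricts the objective-response population to patients with measurable disease at baseline. Section 10.2.3 sets up a separate set for patients whose baseline lesions are evaluable but not measurable.

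**The concern.** The second sentence of the cap goes further than the first. The first rules out CR, which follows from the CR definition. The second makes SD the ceiling, which also rules out PR. The PR condition on non-measurable disease has work to do only if PR is possible while such disease persists; under the cap it is redundant. Two readers can therefore score the same scan as PR and as SD, each following the text.

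Objective response is the outcome of the logistic regression on neoantigen burden (10.3.2). It defines the groups in the responder versus non-responder comparison of symptom severity and interference (10.3.2.1), and it enters the exploratory immune correlates (10.3.5). Scoring true partial responders as SD removes events from these analyses and places those patients in the comparison group, which blurs the contrast being sought.

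**Working it through.** The plan states no figure on this point, so there is none to reproduce. The check sets the rules side by side and then looks at scale and scan timing.

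**1. The conflict, with no extra assumption.** Take a patient with one measurable lesion that goes from 30 × 30 mm to 15 × 15 mm, and a separate lesion under 10 mm that does not change. Suppose the other PR conditions (duration, no new lesions, same technique, steroids, T2/FLAIR, clinical status) are met.

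- Product of diameters: 30 × 30 = 900 mm²; 15 × 15 = 225 mm². Decrease = 1 − 225/900 = 75%, above the 50% threshold.
- Non-measurable disease has not progressed, so the PR list gives PR.
- The Appendix D PR column also gives PR.
- Non-measurable disease is still present, so the cap gives SD.

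The SD definition in 6.3.2.1 does not settle the matter. It excludes anyone who qualifies for PR, and whether this patient qualifies is the question in dispute.

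**2. A wider effect, conditional on one reading of 6.3.1.** If a target lesion that shrinks below 10 mm is itself treated as non-measurable, the cap also catches deep responses.

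| Baseline | Follow-up | Decrease in product |
|---|---|---|
| 15 × 15 mm | 9 × 9 mm | 1 − 81/225 = 64% |
| 20 × 20 mm | 9 × 9 mm | 1 − 81/400 = 80% |
| 30 × 30 mm | 9 × 9 mm | 1 − 81/900 = 91% |
| 40 × 30 mm | 9 × 8 mm | 1 − 72/1200 = 94% |

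All four exceed 50% and would be scored SD. On that reading, 30 × 30 to 9 × 9 mm (91%) ranks below 30 × 30 to 15 × 15 mm (75%) with no other lesion.

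**3. Scale.** Inputs: the maximum of 59 patients (10.1.1.1), and the 8% response rate that 1.2.4 reports for nivolumab in recurrent glioblastoma, assumed to apply here, with 5% to 20% as a range.

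- Expected responders = rate × 59: 3.0 at 5%, 4.7 at 8%, 8.8 at 15%, 11.8 at 20%.
- One misclassified responder is 1/4.7 = 21% of events at 8%, about a third at 5%, and about a twelfth at 20%.
- If half were scored SD (illustrative only), 1.5, 2.4, 4.4 and 5.9 would remain.

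**4. The primary endpoint.** CR, PR and SD all count as progression-free. Moving a patient from PR to SD changes neither PFS6 nor the stage I and final decision rules.

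**5. Confirmation timing.** Scheduled on-treatment MRIs are 8 × 7 = 56 days apart, or 56 − 14 = 42 to 56 + 14 = 70 days when both windows are used. None falls at 28 days, but all fall later than 28 days. The MRI 60 (±14) days after the last dose can also serve. After full treatment, counting the first dose as day 0, the last dose is on day 420, that MRI on day 480 and the week-64 scan on day 448, a gap of 32 days (11 to 53 with windows). The same nominal gap arises after any last dose in an even cycle from 4 to 16.

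**The case against.** The strongest reply is that the cap belongs to the CR criteria and was probably meant for patients who had only non-measurable disease at baseline, whom 10.2.3 handles separately. On that view the PR list and Appendix D show the true intent, and only one loosely worded sentence is at fault. This is plausible, but the text does not say it. The word *residual* describes what remains after treatment and reaches patients with measurable baseline disease, who are the patients in the objective-response population. The ambiguity stands.

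Other parts of the reply are right and limit the point.

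- A reader might infer that the plan ranks a 91% shrinkage below a 75% one. That needs a step the documents do not state: that a baseline target lesion becomes non-measurable once it falls below 10 mm. PR is a change from baseline in the measurable lesions, and 6.3.1 asks for each lesion to be assessed the same way at baseline and follow-up. Both fit continued tracking of the same lesion.
- A reader might infer that no response can ever be confirmed, because no MRI is scheduled exactly four weeks after a response scan. The criteria do not support this. CR is worded "Complete disappearance of all enhancing measurable and non-measurable disease sustained for at least 4 weeks", and PR carries the same minimum duration, so the next 8-week MRI satisfies it.
- Response is not the only outcome for neoantigen burden. Section 10.3.2 also specifies a proportional hazards model for PFS, and 10.3.5 does the same for the immune measures. Those models are unaffected.
- The 8% rate comes from a different population, 59 is a ceiling rather than the response-evaluable number, and with about five events the logistic model is fragile whatever the cap says.
- The reviewed text of Appendix D stops after the table, so only the table's PR column is relied on here.

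**Conclusion.** The conflict between the cap and the PR criteria is real and needs no assumption beyond the text of 6.3.2.1. Applied literally, the cap scores SD for a patient who meets every PR criterion while a small lesion persists unchanged. The extension to deep shrinkage below 10 mm holds only if such lesions are reclassified.

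The number of patients affected is unknown, and no document shows a read scored under either rule. With 3.0 to 11.8 expected responders under the assumed rates, even one changed classification is a noticeable share of the events. The consequence stays within objective response and the secondary, patient-reported and exploratory analyses that use it. PFS6, its decision rules, sample size and power are untouched.

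The confirmation wording is a minor ambiguity. The documents do not support a conclusion that confirmed responders would be zero.

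**What to change.** - In 6.3.2.1, limit the cap to what the CR definition implies. For example: *A patient with measurable disease at baseline whose non-measurable disease persists is not a CR, but is a PR if every PR criterion is met.*
- Leave patients with only non-measurable baseline disease to 10.2.3. Do not add a rule barring them from CR: the documents give no basis for one, and if all their lesions disappear nothing residual is left.
- State whether a target lesion that shrinks below 10 mm stays in the sum of products. This closes the reading in step 2 of the working.
- As a clarification, reword the confirmation sentence for CR and PR so that it matches the four-week minimum already stated and the next scheduled MRI counts.
- Rescore existing reads under the clarified rule before response is analysed against neoantigen burden, symptom scores or immune measures. Stage I of the NHMP cohort had already been assessed (1.2.7), so some reads exist.

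The cost is a few sentences in 6.3.1 and 6.3.2.1 and the rescoring. No scans are added, and the sample size and decision rules stay as they are.

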6.3.3 Duration of Response

Duration of overall response: The duration of overall response is measured from the time measurement criteria are met for CR or PR (whichever is first recorded) until the first date that recurrent or progressive disease is objectively documented (taking as reference for progressive disease the smallest measurements recorded since the treatment started).

The duration of overall CR is measured from the time measurement criteria are first met for CR until the first date that progressive disease is objectively documented.

Duration of stable disease: Stable disease is measured from the start of the treatment until the criteria for progression are met, taking as reference the smallest measurements recorded since the treatment started, including the baseline measurements.

6.3.4 Progression-free survival

Progression free survival is defined from the day of study entry until imaging is confirmed to show disease progression. Given the anticipated high rate of pseudo progression, patients with worsening lesions but without significant clinical decline may continue on treatment at the PI discretion. Subsequent confirmation of disease progression will mandate that the date of progression be defined as the date imaging worsening was first discovered. Patients who undergo diagnostic biopsy or resection uncovering evidence of pseudo progression will NOT be declared as having disease progression and will be able to resume protocol treatment.

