⁷ MRI of brain with gadolinium at screening/baseline and every 8 (+/- 7 days) weeks after beginning of treatment and at 60 (+/- 14 days) day follow up visit after last dose of Nivolumab. Note: if treatment was discontinued because of progression, the 60 days imaging is not necessary. Subjects taken off treatment before completion of 1 year of treatment and without PD at the 28-Day Safety Follow-up visit will be followed till disease progression (MRI scans every 8 (+/- 7 days) weeks with the first assessment 8 weeks after the previous tumor assessment) or 1 year after start of treatment whatever comes first.

⁸ Blood samples will be drawn prior to the initiation of treatment of cycle 1, 2, 3, 5, 7, 9, 11, 13, 15 or until disease progression, whatever comes first. Blood samples will be collected at treatment discontinuation and if patient undergoes surgical procedure after treatment discontinuation, blood samples will be collected for analysis. Also, at the 60 (+/- 14 days) day follow up visit.

⁹ At baseline and then within 7 days prior to each imaging study. After disconnection of treatment should be completed every 6 months. MDASI-BT may be completed electronically. MDASI completed within 14 days prior to treatment will be considered baseline.

¹⁰ Follow up visits are planned to be performed at 60 (+/- 14 days) and 100 (+/- 14 days) days after the last dose of Nivolumab to evaluate patient's safety. After this visit, subjects will be followed every 6 months (\pm 1 month) for survival by phone call or e-mail. Note: Subjects taken off treatment before completion of 1 year of treatment and without PD at the 28-Day Safety Follow-up, will be invited for MRI evaluations every 8 (+/- 7 days) weeks until PD or 1 year after start of treatment whatever comes first.

¹¹ If subjects are unable or not willing to come to NIH for follow up visits, they will be followed by phone call or e-mail for AEs and survival.

¹² Weight needs to be recorded once per cycle of infusion.

Abbreviated Title: Ph II Nivo IDH-mutant Gliomas

Version Date: 03/24/2023

¹³ If patient undergoes surgical procedure after treatment discontinuation, tumor tissue will be collected for analysis. Tumor sample obtained at disease progression, if available.

¹⁴ Optional. Height may be taken at any timepoint during the study, at the discretion of the investigator.

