8.4 WAIVER OF EXPEDITED REPORTING TO CCR

As death due to disease progression is part of the study objectives (PFS), and captured as an endpoint in this study, they will not be reported in expedited manner to the sponsor. However, if there is evidence suggesting a causal relationship between the study drug and the event, report the event in an expedited manner according to section [8.3](#).

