16.4 APPENDIX D: RANO CRITERIA AND iRANO TREATMENT ALGORITHM

Modified RANO Response Criteria				
	CR	PR	SD	PD#
T1-Gd +	None	≥50% decrease	<50% decrease- <25% increase	≥25% increase including new lesion(s)*
T2/FLAIR	Stable or decrease	Stable or decrease	NA	NA
New Lesion	None	None	None	Present (contributing to lesion size)*
Corticosteroids	None	Stable or decrease	Stable or decrease	Stable or increasing
Clinical Status	Stable or increase	Stable or increase	Stable or increase	Decrease*
Requirement for Response	All	All	All	Any*

CR=complete response; **PR**=partial response; **SD**=stable disease; **PD**=progressive disease; **NA**=not applicable

#: Progression occurs when any of the criteria with * is present; radiologic confirmation of progression is permitted as described below

Increase in corticosteroids alone will not be taken into account in determining progression in the absence of persistent clinical deterioration

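### Section 6.3.4 ends PFS only at confirmed imaging progression, which conflicts with 6.3.2, Appendix D and 8.4, and no text says which governs the PFS6 counts

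*Combined protocol and SAP*

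**What the plan says.** The primary endpoint is PFS at 6 months (10.1.1). PFS itself is defined once, in 6.3.4: "Progression free survival is defined from the day of study entry until imaging is confirmed to show disease progression". The rest of 6.3.4 deals with pseudoprogression: staying on treatment, dating confirmed progression back to the first worsening, and not counting cases where biopsy or resection shows pseudoprogression. Clinical decline appears there only as a condition on continuing treatment. Death does not appear.

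Other sections describe progression more broadly:

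- 6.3: "Response and progression will be evaluated in this study using the iRANO (Immunotherapy Response Assessment in Neuro-oncology) criteria".
- 6.3.2.1: any one criterion is enough for PD. The list includes "Clear clinical deterioration not attributable to other causes apart from the tumor" and "Failure to return for evaluation due to death or deteriorating condition".
- Appendix D: "Progression occurs when any of the criteria with * is present". The starred entries include decreased clinical status.
- 8.4: "As death due to disease progression is part of the study objectives (PFS), and captured as an endpoint in this study".

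Section 10 counts patients who have progressed (HMP stage I) or who are progression-free (HMP final rule and both NHMP rules). It refers to neither 6.3.2 nor 6.3.4 and gives no event or censoring rule. Section 10.1.1.1 requires patients with at least one cycle, meaning two infusions. Section 10.3.1 names no analysis set for PFS6.

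**The concern.** The patients on whom the definitions differ are true failures: those who die or decline before a scan can confirm progression. The plan schedules MRI every 8 weeks. Footnotes 7 and 10 of the study calendar extend this to patients who left treatment early without PD ("will be followed till disease progression (MRI scans every 8 (+/- 7 days) weeks", with a one-year limit). That limits the number affected but cannot help a patient who dies or deteriorates before the next scan.

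Each cohort is judged on a small count: at least 6 of 29 (HMP) and at least 10 of 30 (NHMP). One patient classified differently can change a decision. The same definition feeds the Kaplan-Meier and log-rank analyses in 10.3.1 and 12-month PFS in 10.3.2, where a death without a confirming scan would be censored if 6.3.4 were applied as worded. Section 1.2.7 already reports 6 of 15 NHMP patients progression-free without saying which definition was used, and that count carries into the final 10-of-30 decision.

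**Working it through.** **Step 1. The definitions side by side.**

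| Course within 6 months | 6.3.4 as worded | 6.3.2 |
|---|---|---|
| Imaging worsens and is later confirmed | Event, dated to first worsening | PD, same dating |
| Imaging worsens, then significant clinical decline before a confirming scan | No event | PD, back-dated |
| Tumour-related clinical decline without confirmed imaging progression | No event | PD |
| Does not return because of death or decline | No event | PD |

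Appendix D agrees with 6.3.2 on clinical decline; its table does not list death. Section 8.4 agrees on death, but only death due to progression. No text ranks these sections.

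**Step 2. Reproduce the design figures.** Inputs from 10.1.1:

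- HMP: p0 = 0.10, p1 = 0.30; continue with at least 2 of 10, success with at least 6 of 29.
- NHMP: p0 = 0.186, p1 = 0.386; continue with at least 3 of 15, success with at least 10 of 30.

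With n1 and r1 for stage I, n2 further patients and final threshold r:

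P(success) = sum over x from r1 to n1 of P(X1 = x) × P(X2 ≥ r − x), where X1 ~ Bin(n1, p) and X2 ~ Bin(n2, p).

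HMP at p = 0.10:

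- x = 2: 0.19371 × 0.11500 = 0.02228
- x = 3: 0.05740 × 0.29456 = 0.01691
- x = 4: 0.01116 × 0.57974 = 0.00647
- x = 5: 0.00149 × 0.86491 = 0.00129
- x ≥ 6: 0.00015
- Sum: 0.0471

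HMP power at 0.30 is 0.805. NHMP type I error is 0.0389 and power 0.775, matching the 77.5% in 1.2.7. These figures assume that every 6-month failure is counted as one.

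**Step 3. One stage II failure scored progression-free (scenario).** The stage I gate is unchanged; the final threshold in effect falls by one.

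- HMP (at least 2 of 10, then at least 5 of 29) at 0.10: 0.05706 + 0.03327 + 0.00965 + 0.00164 = 0.102, against 0.047.
- NHMP (at least 3 of 15, then at least 9 of 30) at 0.186: 0.087, against 0.039.

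**Step 4. Early failures dropped and replaced (scenario).** Suppose a share d of treated patients fail before the second infusion and are replaced. The null rate among those kept is p0 / (1 − d). The documents give no d; 5% and 10% are assumptions.

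| d | HMP null rate | HMP type I error | NHMP null rate | NHMP type I error |
|---|---|---|---|---|
| 5% | 0.10/0.95 = 0.1053 | 0.058 | 0.186/0.95 = 0.1958 | 0.053 |
| 10% | 0.10/0.90 = 0.1111 | 0.071 | 0.186/0.90 = 0.2067 | 0.072 |

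**Step 5. The NHMP interim count.** The current stage I gate is 3 and 6 were reported. The gate would fail only if four of the six were reclassified (6 − 4 = 2). The decision to continue is therefore robust; what matters is the number carried into the final count.

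**The case against.** The best defence is that the plan already covers these patients. Section 6.3 applies iRANO to progression throughout the study, 6.3.2 lists failure to return because of death or decline as PD, and 8.4 treats death from progression as part of PFS. The death criterion in 6.3.2 carries no restriction on cause, whereas the neighbouring clinical criterion does. On this view 6.3.4 is mainly a dating rule for imaging events under pseudoprogression.

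Much of this stands, and it removes most of the conflict. It does not remove all of it. Section 6.3.4 is the specific provision for PFS, is narrower, and is not made subject to 6.3.2. Death enters 6.3.2 only as a reason for missing an evaluation, which is not the same as stating that death from any cause is a PFS event.

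Three stronger inferences are tempting and are not supported:

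- That patients who die will be scored progression-free. No text directs this; censoring or non-classification is the more natural result of 6.3.4. Step 3 also fixes exactly one such error per trial, so it is a scenario and not an operating characteristic of the design.
- That early failures are being dropped. The two-infusion wording in 10.1.1.1 could be read that way, and the early-progression note in 10.2.2 covers objective response only, but nothing orders their exclusion. Section 1.2.7 speaks of 15 accrued and 15 treated NHMP patients, which points the other way.
- That the 6 of 15 count is wrong. The documents do not say which definition produced it.

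The copy available contains the Appendix D table but not the algorithm named in its title, so nothing here relies on what that algorithm might omit.

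**Conclusion.** The point holds as a conflict between stated rules that should be fixed; it is not a demonstrated bias. The only PFS definition omits clinical progression and death, three other sections include one or both, and nothing says which applies to PFS6. The textual conflict is certain. Its numerical effect is unknown because the documents give no rate of failure without a confirming scan. The illustrative type I errors are 0.102 (HMP) and 0.087 (NHMP) for one mis-scored stage II failure, and 0.058 to 0.071 (HMP) and 0.053 to 0.072 (NHMP) for early failures replaced at an assumed 5% to 10%. If 6.3.2 governs and every treated patient counts, the errors stay at 0.047 and 0.039.

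**What to change.** 1. In 6.3.4, define PFS as the time from study entry to the earlier of PD by any 6.3.2 criterion (back-dated when confirmed) or death from any cause. Keep the existing biopsy and resection exception for pseudoprogression. Cite this definition in 10.1.1 and 10.3.1.
2. In 10.3.1, state that treated patients who die or progress before the second infusion count as not progression-free.
3. Confirm that the 6 of 15 NHMP count holds under this definition, and disclose that the clarification came after that count was known.

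When citing 6.3.2, reconcile its enlargement threshold (more than 25%) with that in Appendix D (25% or more).

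The cost is a wording amendment and a re-derivation of PFS6 from data already held. No boundary or sample size changes. Observed PFS6 may be slightly lower; adding events can only keep or reduce the 6 of 15, so the late timing cannot favour the drug.

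How to treat unknown or non-evaluable 6-month status is a separate choice and not part of this error. It includes scans after a steroid decrease, where 6.3.2 says the patient "cannot be classified as PD and should be classified as non-evaluable".

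### Sections 6.3.4 and 6.3.2.1 back-date a confirmed progression to different events, so one patient can be both a PFS6 success and a PFS6 failure

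*Combined protocol and SAP*

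**What the plan says.** Three places in the combined protocol and SAP bear on the date of progression.

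- **Section 6.3.4** defines the endpoint: "Progression free survival is defined from the day of study entry until imaging is confirmed to show disease progression". Patients whose lesions worsen without marked clinical decline may stay on treatment at the investigator's discretion. Then: "Subsequent confirmation of disease progression will mandate that the date of progression be defined as the date imaging worsening was first discovered". It adds that "Patients who undergo diagnostic biopsy or resection uncovering evidence of pseudo progression will NOT be declared as having disease progression".
- **Section 6.3.2.1** lists the progression criteria, the first being "> 25% increase in sum of the products of perpendicular diameters of enhancing lesions", measured from the smallest size or from baseline. On deferral it says: "Classification of progressive disease may be deferred for up to three months for patients with initial radiographic findings consistent with progressive disease". The date is then fixed "if follow-up imaging after three months confirms progression or if the patient experiences significant clinical decline at any time", in which case "the date of actual progression will be back-dated to the first date that the patient met criteria for progression".
- **Appendix D** tabulates the modified RANO criteria. Stable disease includes growth below 25%. Progression is growth of 25% or more, whereas 6.3.2.1 asks for more than 25%.

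PFS at 6 months is the primary endpoint and supplies the counts for both two-stage rules (sections 10.1.1 and 10.3.4).

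**The concern.** The two back-dating sentences serve the same purpose but point to different events. A scan can look worse without meeting the progression criteria, and Appendix D calls such a scan stable disease. Where sub-threshold growth came before month 6 and the criteria were first met after it, the choice of section decides whether the patient counts as progression-free.

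There is also a gap. Suppose a lesion worsens, a later scan no longer meets the criteria, and progression is confirmed much later. Neither passage says whether the date is the early worsening or the later growth. The protocol expects pseudoprogression to be common, so this case is foreseeable.

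The margins are small. The HMP cohort needs 6 of 29 and the NHMP cohort 10 of 30. Section 1.2.7 reports 6 of 15 NHMP patients progression-free at stage I, exactly the number the rule then in force required. Those patients remain among the 30.

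**Working it through.** **1. The two anchors on one record (invented for illustration).** Scans are every 8 weeks (section 3.5). Six months is 365.25 / 2 / 7 = 26.1 weeks, so scans at weeks 8, 16 and 24 fall before it. Take a baseline area of 400 mm², stable steroids and stable clinical status.

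| Week | Area (mm²) | Change from baseline | Appendix D |
|---|---|---|---|
| 8 | 460 | 60/400 = +15% | stable |
| 16 | 480 | 80/400 = +20% | stable |
| 24 | 490 | 90/400 = +22.5% | stable |
| 32 | 560 | 160/400 = +40% | progression, confirmed later |

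Under 6.3.2.1 the date is week 32, a PFS6 success. Under 6.3.4 read literally it is week 8, a failure. Section 6.3.3 runs stable disease until the progression criteria are met, so the same record could show 32 weeks of stable disease and 8 weeks of PFS.

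**2. Reproducing the design figures.** Inputs from section 10.1.1: HMP continues with at least 2 of 10 progression-free (stop if 9 or more progress) and succeeds with at least 6 of 29, at 0.10 against 0.30. NHMP continues with at least 3 of 15 and succeeds with at least 10 of 30, at 0.186 against 0.386. The probability of success is

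P(p) = Σ over x ≥ r1 of Bin(x; n1, p) × Pr[Bin(n − n1, p) ≥ r − x].

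- HMP: type I error 0.0471, power 0.805. This agrees with the stated 0.05 and 0.8.
- NHMP: type I error 0.0389, power 0.775. This agrees with the 77.5% in section 1.2.7, not the 0.8 in section 10.1.1.

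**3. Sensitivity.** Let f be the share of true 6-month successes re-dated to before month 6. The documents give no value, so f is an assumption. Replace p by p(1 − f).

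| f | HMP p1(1 − f) | HMP power | HMP type I error | NHMP p1(1 − f) | NHMP power | NHMP type I error |
|---|---|---|---|---|---|---|
| 0 | 0.300 | 0.805 | 0.0471 | 0.386 | 0.775 | 0.0389 |
| 5% | 0.285 | 0.766 | 0.0382 | 0.367 | 0.705 | 0.0282 |
| 10% | 0.270 | 0.720 | 0.0305 | 0.347 | 0.625 | 0.0199 |

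At f = 10% the expected number re-dated is 29 × 0.30 × 0.10 = 0.87 (HMP) and 30 × 0.386 × 0.10 = 1.16 (NHMP), about one patient per cohort.

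The table applies f at both stages. If re-dating came only after the stage I look, stage I would use p and only the final count would be thinned by (1 − f). Power at f = 5% and 10% is then 0.782 and 0.752 (HMP), 0.707 and 0.628 (NHMP).

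**4. One patient at the boundary.** Under the alternatives, the chance of passing stage I and finishing with exactly the minimum number of successes, Σ over x ≥ r1 of Bin(x; n1, p1) × Bin(r − x; n − n1, p1), is 0.066 for HMP and 0.125 for NHMP. There, one re-dated patient reverses the conclusion.

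**The case against.** The best defence is that worsening in 6.3.4 means worsening at the level of progression. The sentence before it lets patients with worsening lesions continue at the investigator's discretion, and a patient with stable disease would need no such permission. Section 6.3 also makes iRANO govern progression. This is probably what was intended, and it is why the repair is small. But it is an inference: the section that defines PFS does not say it, and no passage ranks 6.3.2.1 above 6.3.4.

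Several stronger readings are tempting and are not supported.

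- *The plan has no threshold for back-dating.* It has one, in 6.3.2.1. The defect is the conflict.
- *No confirmation is needed.* Both passages require it. What is missing is a rule for an intervening scan that no longer meets the criteria. Section 6.3 refers to Appendix D for the full explanation, and its algorithm is not shown in this text, so the rule may be there.
- *Only pseudoprogression proven by tissue is exempt.* Worsening that is never confirmed is not progression under 6.3.4. The tissue sentence adds a route and does not exclude others.
- *Clinical decline at any later time re-dates to the first bad scan.* That phrase sits in a sentence about patients whose classification is deferred and is naturally limited to them.
- *Any re-dating across month 6 is an error.* A scan at week 16 or 24 that met the criteria and was later confirmed is meant to count as a failure under both sections.

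**Conclusion.** The concern holds as a conflict between two written rules for the primary endpoint, together with silence, in the text available, on intervening scans. The conflict does not depend on the missing algorithm; the silence may.

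Its size cannot be estimated from the documents, which give neither growth rates nor a level at which a reader would call a scan worse. On an assumed 5% to 10% of true successes re-dated, with f applied at both stages, HMP loses about 4 to 9 points of power and NHMP about 7 to 15. Type I error falls as well, so the risk is a missed effect, not a false claim of promise. If the trial already reads 6.3.4 as requiring the 6.3.2.1 criteria, f from this source is zero and only the wording needs repair. It should still be settled before the final PFS6 counts are made.

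**What to change.** 1. In 6.3.4, replace the end of the back-dating sentence so that the date of progression is *the date of the first scan that met the 6.3.2.1 criteria for progression and was subsequently confirmed*.
2. Make the 25% wording the same in 6.3.2.1 and Appendix D.
3. State, consistently with the iRANO algorithm, that an earlier worsening that was not confirmed is not the progression date.
4. Apply this to all patients, including those already treated. Record it as a clarification made after the NHMP stage I result was known. If any patient's PFS6 classification differs between the two anchors, report PFS6 under both.

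The wording on clinical decline and on stopping treatment should stay as it is, beyond noting that the passages must be reconciled.

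The cost is a few lines of protocol text and a re-check of existing progression dates. No new data are needed, and the sample sizes, cut-offs and operating characteristics do not change.
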